Hearing Loss ≥ 12 years of age	NA	Hearing aid or intervention not indicated	Hearing aid or intervention indicated	Profound bilateral hearing loss (> 80 dB at 2 kHz and above) OR Non-serviceable hearing (i.e., >50 dB audiogram and <50% speech discrimination)
< 12 years of age (based on a 1, 2, 3, 4, 6 and 8 kHz audiogram)	> 20 dB hearing loss at ≤ 4 kHz	> 20 dB hearing loss at > 4 kHz	> 20 dB hearing loss at ≥ 3 kHz in one ear with additional speech language related services indicated (where available) OR Hearing loss sufficient to indicate therapeutic intervention, including hearing aids	Audiologic indication for cochlear implant and additional speech- language related services indicated (where available)
Tinnitus	Symptoms causing no or minimal interference with usual social & functional activities with intervention not indicated	Symptoms causing greater than minimal interference with usual social & functional activities with intervention indicated	Symptoms causing inability to perform usual social & functional activities	NA
Uveitis	No symptoms AND Detectable on examination	Anterior uveitis with symptoms OR Medical intervention indicated	Posterior or pan- uveitis OR Operative intervention indicated	Disabling visual loss in affected eye(s)
Vertigo	Vertigo causing no or minimal interference with usual social & functional activities	Vertigo causing greater than minimal interference with usual social & functional activities	Vertigo causing inability to perform usual social & functional activities	Disabling vertigo causing inability to perform basic self-care functions
Visual Changes (assessed from baseline)	Visual changes causing no or minimal interference with usual social & functional activities	Visual changes causing greater than minimal interference with usual social & functional activities	Visual changes causing inability to perform usual social & functional activities	Disabling visual loss in affected eye(s)

Systemic

PARAMETER	GRADE 1 MILD	GRADE 2 MODERATE	GRADE 3 SEVERE	GRADE 4 POTENTIALLY LIFE- THREATENING
Acute Allergic Reaction	Localized urticaria (wheals) with no medical intervention indicated	Localized urticaria with intervention indicated OR Mild angioedema with no intervention indicated	Generalized urticaria OR Angioedema with intervention indicated OR Symptoms of mild bronchospasm	Acute anaphylaxis OR Life-threatening bronchospasm OR Laryngeal edema
Chills	Symptoms causing no or minimal interference with usual social & functional activities	Symptoms causing greater than minimal interference with usual social & functional activities	Symptoms causing inability to perform usual social & functional activities	NA
Cytokine Release Syndrome ⁸	Mild signs and symptoms AND Therapy (i.e., antibody infusion) interruption not indicated	Therapy (i.e., antibody infusion) interruption indicated AND Responds promptly to symptomatic treatment OR Prophylactic medications indicated for ≤ 24 hours	Prolonged severe signs and symptoms OR Recurrence of symptoms following initial improvement	Life-threatening consequences (e.g., requiring pressor or ventilator support)
Fatigue or Malaise Report only one	Symptoms causing no or minimal interference with usual social & functional activities	Symptoms causing greater than minimal interference with usual social & functional activities	Symptoms causing inability to perform usual social & functional activities	Incapacitating symptoms of fatigue or malaise causing inability to perform basic self-care functions
Fever (non-axillary temperatures only)	38.0 to < 38.6°C or 100.4 to < 101.5°F	\geq 38.6 to < 39.3°C or \geq 101.5 to < 102.7°F	\geq 39.3 to < 40.0°C or \geq 102.7 to < 104.0°F	\geq 40.0°C or \geq 104.0°F
Pain ⁹ (not associated with study agent injections and not specified elsewhere) Specify location	Pain causing no or minimal interference with usual social & functional activities	Pain causing greater than minimal interference with usual social & functional activities	Pain causing inability to perform usual social & functional activities	Disabling pain causing inability to perform basic self-care functions OR Hospitalization indicated

⁸ Definition: A disorder characterized by nausea, headache, tachycardia, hypotension, rash, and/or shortness of breath.

⁹ For pain associated with injections or infusions, see the Site Reactions to Injections and Infusions section

Systemic

PARAMETER	GRADE 1 MILD	GRADE 2 MODERATE	GRADE 3 SEVERE	GRADE 4 POTENTIALLY LIFE- THREATENING
Serum Sickness ¹⁰	Mild signs and symptoms	Moderate signs and symptoms AND Intervention indicated (e.g., antihistamines)	Severe signs and symptoms AND Higher level intervention indicated (e.g., steroids or IV fluids)	Life-threatening consequences (e.g., requiring pressor or ventilator support)
Underweight ¹¹ > 5 to 19 years of age	WHO BMI z-score < -1 to -2	WHO BMI z-score < -2 to -3	WHO BMI z-score < -3	WHO BMI z-score < -3 with life-threatening consequences
2 to 5 years of age	WHO BMI z-score < -1 to -2	WHO Weight-for- height z-score < -2 to -3	WHO Weight-for- height z-score < -3	WHO Weight-for-height z-score < -3 with life- threatening consequences
< 2 years of age	WHO BMI z-score < -1 to -2	WHO Weight-for- length z-score < -2 to -3	WHO Weight-for- length z-score < -3	WHO Weight-for-length z-score < -3 with life- threatening consequences
Unintentional Weight Loss (excludes postpartum weight loss)	NA	5 to < 9% loss in body weight from baseline	≥ 9 to < 20% loss in body weight from baseline	≥ 20% loss in body weight from baseline OR Aggressive intervention indicated (e.g., tube feeding, total parenteral nutrition)

¹⁰ Definition: A disorder characterized by fever, arthralgia, myalgia, skin eruptions, lymphadenopathy, marked discomfort, and/or

dyspnea. ¹¹ WHO reference tables may be accessed by clicking the desired age range or by accessing the following URLs: http://www.who.int/growthref/who2007_bmi_for_age/en/ for participants > 5 to 19 years of age and $http://www.who.int/childgrowth/standards/chart_catalogue/en/ \ for \ those \leq 5 \ years \ of \ age.$

Urinary

PARAMETER	GRADE 1 MILD	GRADE 2 MODERATE	GRADE 3 SEVERE	GRADE 4 POTENTIALLY LIFE- THREATENING
Urinary Tract Obstruction	NA	Signs or symptoms of urinary tract obstruction without hydronephrosis or renal dysfunction	Signs or symptoms of urinary tract obstruction with hydronephrosis or renal dysfunction	Obstruction causing life-threatening consequences

Site Reactions to Injections and Infusions

PARAMETER	GRADE 1 MILD	GRADE 2 MODERATE	GRADE 3 SEVERE	GRADE 4 POTENTIALLY LIFE- THREATENING
Injection Site Pain or Tenderness Report only one	Pain or tenderness causing no or minimal limitation of use of limb	Pain or tenderness causing greater than minimal limitation of use of limb	Pain or tenderness causing inability to perform usual social & functional activities	Pain or tenderness causing inability to perform basic self-care function OR Hospitalization indicated
Injection Site Erythema or Redness ¹² Report only one > 15 years of age	2.5 to < 5 cm in diameter OR 6.25 to < 25 cm ² surface area AND Symptoms causing no or minimal interference with usual social & functional activities	\geq 5 to < 10 cm in diameter OR \geq 25 to < 100 cm ² surface area OR Symptoms causing greater than minimal interference with usual social & functional activities	\geq 10 cm in diameter OR \geq 100 cm ² surface area OR Ulceration OR Secondary infection OR Phlebitis OR Sterile abscess OR Drainage OR Symptoms causing inability to perform usual social & functional activities	Potentially life- threatening consequences (e.g., abscess, exfoliative dermatitis, necrosis involving dermis or deeper tissue)
≤ 15 years of age	≤ 2.5 cm in diameter	> 2.5 cm in diameter with < 50% surface area of the extremity segment involved (e.g., upper arm or thigh)	≥ 50% surface area of the extremity segment involved (e.g., upper arm or thigh) OR Ulceration OR Secondary infection OR Phlebitis OR Sterile abscess OR Drainage	Potentially life- threatening consequences (e.g., abscess, exfoliative dermatitis, necrosis involving dermis or deeper tissue)
Injection Site Induration or Swelling Report only one > 15 years of age	Same as for Injection Site Erythema or Redness, > 15 years of age	Same as for Injection Site Erythema or Redness, > 15 years of age	Same as for Injection Site Erythema or Redness, > 15 years of age	Same as for Injection Site Erythema or Redness, > 15 years of age
≤15 years of age	Same as for Injection Site Erythema or Redness, ≤ 15 years of age	Same as for Injection Site Erythema or Redness, ≤ 15 years of age	Same as for Injection Site Erythema or Redness, ≤ 15 years of age	Same as for Injection Site Erythema or Redness, ≤ 15 years of age
Injection Site Pruritus	Itching localized to the injection site that is relieved spontaneously or in < 48 hours of treatment	Itching beyond the injection site that is not generalized OR Itching localized to the injection site requiring \geq 48 hours treatment	Generalized itching causing inability to perform usual social & functional activities	NA

¹² Injection Site Erythema or Redness should be evaluated and graded using the greatest single diameter or measured surface area.

Laboratory Values* Chemistries

PARAMETER	GRADE 1 MILD	GRADE 2 MODERATE	GRADE 3 SEVERE	GRADE 4 POTENTIALLY LIFE- THREATENING
Acidosis	NA	$pH \geq 7.3$ to $< LLN$	pH < 7.3 without life- threatening consequences	pH < 7.3 with life- threatening consequences
Albumin, Low (g/dL; g/L)	3.0 to < LLN 30 to < LLN	$\geq 2.0 \text{ to} < 3.0$ $\geq 20 \text{ to} < 30$	< 2.0 < 20	NA
Alkaline Phosphatase, High	1.25 to < 2.5 x ULN	2.5 to < 5.0 x ULN	5.0 to < 10.0 x ULN	\geq 10.0 x ULN
Alkalosis	NA	pH \geq ULN to ≤ 7.5	pH > 7.5 without life- threatening consequences	pH > 7.5 with life- threatening consequences
ALT or SGPT, High Report only one	1.25 to < 2.5 x ULN	2.5 to < 5.0 x ULN	5.0 to < 10.0 x ULN	\geq 10.0 x ULN
Amylase (Pancreatic) or Amylase (Total), High Report only one	1.1 to < 1.5 x ULN	1.5 to < 3.0 x ULN	3.0 to < 5.0 x ULN	\geq 5.0 x ULN
AST or SGOT, High Report only one	1.25 to < 2.5 x ULN	2.5 to < 5.0 x ULN	5.0 to < 10.0 x ULN	\geq 10.0 x ULN
Bicarbonate, Low (mEq/L; mmol/L)	16.0 to < LLN 16.0 to < LLN	11.0 to < 16.0 11.0 to < 16.0	8.0 to < 11.0 8.0 to < 11.0	< 8.0 < 8.0
Bilirubin Direct Bilirubin ¹³ , High > 28 days of age	NA	NA	> ULN with other signs and symptoms of hepatotoxicity.	> ULN with life- threatening consequences (e.g., signs and symptoms of liver failure)
\leq 28 days of age	ULN to $\leq 1 \text{ mg/dL}$	> 1 to ≤ 1.5 mg/dL	$>$ 1.5 to $\leq 2~mg/dL$	>2 mg/dL
Total Bilirubin, High > 28 days of age	1.1 to < 1.6 x ULN	1.6 to < 2.6 x ULN	2.6 to < 5.0 x ULN with other signs and symptoms of hepatotoxicity.	≥ 5.0 x ULN with life- threatening consequences (e.g., signs and symptoms of liver failure).
\leq 28 days of age	See Appendix A. Total Bilirubin for Term and Preterm Neonates	See Appendix A. Total Bilirubin for Term and Preterm Neonates	See Appendix A. Total Bilirubin for Term and Preterm Neonates	See Appendix A. Total Bilirubin for Term and Preterm Neonates

^{*}Reminder: An asymptomatic abnormal laboratory finding without an accompanying AE should not be reported to DAIDS in an expedited time frame unless it meets protocol-specific reporting requirements.

 $^{^{13}}$ Direct bilirubin > 1.5 mg/dL in a participant < 28 days of age should be graded as grade 2, if < 10% of the total bilirubin.

Chemistries

PARAMETER	GRADE 1 MILD	GRADE 2 MODERATE	GRADE 3 SEVERE	GRADE 4 POTENTIALLY LIFE- THREATENING
Calcium, High (mg/dL; mmol/L) ≥ 7 days of age	10.6 to < 11.5 2.65 to < 2.88	11.5 to < 12.5 2.88 to < 3.13	12.5 to < 13.5 3.13 to < 3.38	≥ 13.5 ≥ 3.38
< 7 days of age	11.5 to < 12.4 2.88 to < 3.10	12.4 to < 12.9 3.10 to < 3.23	12.9 to < 13.5 3.23 to < 3.38	≥ 13.5 ≥ 3.38
Calcium (Ionized), High (mg/dL; mmol/L)	> ULN to < 6.0 > ULN to < 1.5	6.0 to < 6.4 1.5 to < 1.6	6.4 to < 7.2 1.6 to < 1.8	$ \geq 7.2 \\ \geq 1.8 $
Calcium, Low (mg/dL; $mmol/L$) \geq 7 days of age< 7 days of age	7.8 to < 8.4 1.95 to < 2.10 6.5 to < 7.5 1.63 to < 1.88	7.0 to < 7.8 1.75 to < 1.95 6.0 to < 6.5 1.50 to < 1.63	6.1 to < 7.0 1.53 to < 1.75 5.50 to < 6.0 1.38 to < 1.50	< 6.1 < 1.53 < 5.50 < 1.38
Calcium (Ionized), Low (mg/dL; mmol/L)	< LLN to 4.0 < LLN to 1.0	3.6 to < 4.0 0.9 to < 1.0	3.2 to < 3.6 0.8 to < 0.9	< 3.2 < 0.8
Cardiac Troponin I, High	NA	NA	NA	Levels consistent with myocardial infarction or unstable angina as defined by the local laboratory
Creatine Kinase, High	3 to < 6 x ULN	6 to < 10x ULN	10 to < 20 x ULN	\geq 20 x ULN
Creatinine, High *Report only one	1.1 to 1.3 x ULN	> 1.3 to 1.8 x ULN OR Increase to 1.3 to < 1.5 x participant's baseline	> 1.8 to < 3.5 x ULN OR Increase to 1.5 to < 2.0 x participant's baseline	\geq 3.5 x ULN OR Increase of \geq 2.0 x participant's baseline
Creatinine Clearance ¹⁴ or eGFR, Low * Report only one	NA	< 90 to 60 ml/min or ml/min/1.73 m ² OR 10 to < 30% decrease from participant's baseline	< 60 to 30 ml/min or ml/min/1.73 m ² OR 30 to < 50% decrease from participant's baseline	< 30 ml/min or ml/min/1.73 m ² OR ≥ 50% decrease from participant's baseline or dialysis needed
Glucose (mg/dL; mmol/L) Fasting, High	110 to 125 6.11 to < 6.95	> 125 to 250 6.95 to < 13.89	> 250 to 500 13.89 to < 27.75	≥ 500 ≥ 27.75
Nonfasting, High	116 to 160 6.44 to < 8.89	> 160 to 250 8.89 to < 13.89	> 250 to 500 13.89 to < 27.75	≥ 500 ≥ 27.75

¹⁴ Use the applicable formula (i.e., Cockcroft-Gault in mL/min or Schwartz, MDRD, CKD-Epi in mL/min/1.73m2). Sites should choose the method defined in their study and when not specified, use the method most relevant to the study population.

^{*}Reminder: Choose the method that selects for the higher grade.

Chemistries

PARAMETER	GRADE 1 MILD	GRADE 2 MODERATE	GRADE 3 SEVERE	GRADE 4 POTENTIALLY LIFE- THREATENING
Glucose, Low (mg/dL; $mmol/L$) ≥ 1 month of age	55 to 64 3.05 to <3.55	40 to < 55 2.22 to < 3.05	30 to < 40 1.67 to < 2.22	< 30 < 1.67
< 1 month of age	50 to 54 2.78 to < 3.00	40 to < 50 2.22 to < 2.78	30 to < 40 1.67 to < 2.22	< 30 < 1.67
Lactate, High	ULN to < 2.0 x ULN without acidosis	\geq 2.0 x ULN without acidosis	Increased lactate with pH < 7.3 without life- threatening consequences	Increased lactate with pH < 7.3 with life- threatening consequences
Lipase, High	1.1 to < 1.5 x ULN	1.5 to < 3.0 x ULN	3.0 to < 5.0 x ULN	\geq 5.0 x ULN
Lipid Disorders (mg/dL; mmol/L) Cholesterol, Fasting, High ≥ 18 years of age	200 to < 240 5.18 to < 6.19	240 to < 300 6.19 to < 7.77	≥ 300 ≥ 7.77	NA
< 18 years of age	170 to < 200 4.40 to < 5.15	200 to < 300 5.15 to < 7.77	≥ 300 ≥ 7.77	NA
LDL, Fasting, High ≥ 18 years of age	130 to < 160 3.37 to < 4.12	160 to < 190 4.12 to < 4.90	≥ 190 ≥ 4.90	NA
> 2 to < 18 years of age	110 to < 130 2.85 to < 3.34	130 to < 190 3.34 to < 4.90	≥ 190 ≥ 4.90	NA
Triglycerides, Fasting, High	150 to 300 1.71 to 3.42	>300 to 500 >3.42 to 5.7	>500 to < 1,000 >5.7 to 11.4	>1,000 >11.4
Magnesium ¹⁵ , Low (mEq/L; mmol/L)	1.2 to $<$ 1.4 0.60 to $<$ 0.70	0.9 to < 1.2 0.45 to < 0.60	0.6 to < 0.9 0.30 to < 0.45	< 0.6 < 0.30
Phosphate, Low (mg/dL; mmol/L) > 14 years of age	2.0 to < LLN 0.65 to < LLN	1.4 to < 2.0 0.45 to < 0.65	1.0 to $<$ 1.4 0.32 to $<$ 0.45	< 1.0 < 0.32
1 to 14 years of age	3.0 to < 3.5 0.97 to < 1.13	2.5 to < 3.0 0.81 to < 0.97	1.5 to < 2.5 0.48 to < 0.81	< 1.5 < 0.48
< 1 year of age	3.5 to < 4.5 1.13 to < 1.45	2.5 to < 3.5 0.81 to < 1.13	1.5 to < 2.5 0.48 to < 0.81	<1.5 < 0.48
Potassium, High (mEq/L; mmol/L)	5.6 to < 6.0 5.6 to < 6.0	6.0 to < 6.5 6.0 to < 6.5	6.5 to < 7.0 6.5 to < 7.0	≥ 7.0 ≥ 7.0
Potassium, Low (mEq/L; mmol/L)	3.0 to < 3.4 3.0 to < 3.4	2.5 to < 3.0 2.5 to < 3.0	2.0 to < 2.5 2.0 to < 2.5	< 2.0 < 2.0

 15 To convert a magnesium value from mg/dL to mmol/L, laboratories should multiply by 0.4114.

Chemistries

PARAMETER	GRADE 1 MILD	GRADE 2 MODERATE	GRADE 3 SEVERE	GRADE 4 POTENTIALLY LIFE- THREATENING
Sodium, High	146 to < 150	150 to $<$ 154	154 to < 160	≥ 160
(mEq/L; mmol/L)	146 to < 150	150 to $<$ 154	154 to < 160	≥ 160
Sodium, Low	130 to < 135	125 to < 130	121 to < 125	≤ 120
(mEq/L; mmol/L)	130 to < 135	125 to < 130	121 to < 125	≤ 120
Uric Acid, High	7.5 to < 10.0	10.0 to $<$ 12.0	12.0 to $<$ 15.0	≥ 15.0
(mg/dL; mmol/L)	0.45 to < 0.59	0.59 to $<$ 0.71	0.71 to $<$ 0.89	≥ 0.89

Hematology

PARAMETER	GRADE 1 MILD	GRADE 2 MODERATE	GRADE 3 SEVERE	GRADE 4 POTENTIALLY LIFE- THREATENING
Absolute CD4+ Count, Low (cell/mm ³ ; cells/L) > 5 years of age (not HIV infected)	300 to < 400 300 to < 400	200 to < 300 200 to < 300	100 to < 200 100 to < 200	< 100 < 100
Absolute Lymphocyte Count, Low (cell/mm ³ ; cells/L) > 5 years of age (not HIV infected)	600 to < 650 0.600 x 10^{9} to < 0.650 x 10^{9}	500 to < 600 $0.500 \times 10^{\circ}$ to < $0.600 \times 10^{\circ}$	350 to < 500 $0.350 \times 10^{9} \text{ to}$ $< 0.500 \times 10^{9}$	< 350 < 0.350 x 10 ⁹
Absolute Neutrophil Count (ANC), Low (cells/mm ³ ; cells/L) > 7 days of age	800 to 1,000 0.800 x 10° to 1.000 x 10°	600 to 799 0.600 x 10° to 0.799 x 10°	400 to 599 0.400 x 10° to 0.599 x 10°	< 400 < 0.400 x 10 ⁹
2 to 7 days of age	1,250 to 1,500 1.250 x 10° to 1.500 x 10°	1,000 to 1,249 1.000 x 10° to 1.249 x 10°	750 to 999 0.750 x 10^{9} to 0.999 x 10^{9}	< 750 < 0.750 x 10 ⁹
$\leq 1 day of age$	4,000 to 5,000 4.000 x 10 ⁹ to 5.000 x 10 ⁹	3,000 to 3,999 3.000 x 10° to 3.999 x 10°	1,500 to 2,999 1.500 x 10° to 2.999 x 10°	< 1,500 < 1.500 x 10°
Fibrinogen, Decreased (mg/dL; g/L)	100 to < 200 1.00 to < 2.00 OR 0.75 to < 1.00 x LLN	75 to < 100 0.75 to < 1.00 OR ≥ 0.50 to < 0.75 x LLN	50 to < 75 0.50 to < 0.75 OR 0.25 to < 0.50 x LLN	< 50 < 0.50 OR < 0.25 x LLN OR Associated with gross bleeding
Hemoglobin ¹⁶ , Low $(g/dL; mmol/L)^{17}$ ≥ 13 years of age (male only)	10.0 to 10.9 6.19 to 6.76	9.0 to < 10.0 5.57 to < 6.19	7.0 to < 9.0 4.34 to < 5.57	< 7.0 < 4.34
≥13 years of age (female only)	9.5 to 10.4 5.88 to 6.48	8.5 to < 9.5 5.25 to < 5.88	6.5 to < 8.5 4.03 to < 5.25	< 6.5 < 4.03

¹⁶ Male and female sex are defined as sex at birth. For transgender participants ≥13 years of age who have been on hormone therapy for more than 6 consecutive months, grade hemoglobin based on the gender with which they identify (i.e., a transgender female should be graded using the female sex at birth hemoglobin laboratory values).

 17 The most commonly used conversion factor to convert g/dL to mmol/L is 0.6206. For grading hemoglobin results obtained by an analytic method with a conversion factor other than 0.6206, the result must be converted to g/dL using appropriate conversion factor for the particular laboratory.

Hematology

PARAMETER	GRADE 1 MILD	GRADE 2 MODERATE	GRADE 3 SEVERE	GRADE 4 POTENTIALLY LIFE- THREATENING
57 days of age to < 13 years of age (male and female)	9.5 to 10.4 5.88 to 6.48	8.5 to < 9.5 5.25 to < 5.88	6.5 to < 8.5 4.03 to < 5.25	< 6.5 < 4.03
36 to 56 days of age (male and female)	8.5 to 9.6 5.26 to 5.99	7.0 to < 8.5 4.32 to < 5.26	6.0 to < 7.0 3.72 to < 4.32	< 6.0 < 3.72
22 to 35 days of age (male and female)	9.5 to 11.0 5.88 to 6.86	8.0 to < 9.5 4.94 to < 5.88	6.7 to < 8.0 4.15 to < 4.94	< 6.7 < 4.15
8 to \leq 21 days of age (male and female)	11.0 to 13.0 6.81 to 8.10	9.0 to < 11.0 5.57 to < 6.81	8.0 to < 9.0 4.96 to < 5.57	< 8.0 < 4.96
≤7 days of age (male and female)	13.0 to 14.0 8.05 to 8.72	10.0 to < 13.0 6.19 to < 8.05	9.0 to < 10.0 5.59 to < 6.19	< 9.0 < 5.59
INR, High (not on anticoagulation therapy)	1.1 to < 1.5 x ULN	1.5 to < 2.0 x ULN	2.0 to < 3.0 x ULN	\geq 3.0 x ULN
Methemoglobin (% hemoglobin)	5.0 to < 10.0%	10.0 to < 15.0%	15.0 to < 20.0%	≥ 20.0%
PTT, High (not on anticoagulation therapy)	1.1 to < 1.66 x ULN	1.66 to < 2.33 x ULN	2.33 to < 3.00 x ULN	≥ 3.00 x ULN
Platelets, Decreased (cells/mm ³ ; cells/L)	$ \begin{array}{l} 100,000 \text{ to} \\ < 125,000 \\ 100.000 \ x \ 10^{9} \ to \\ < 125.000 \ x \ 10^{9} \end{array} $	50,000 to < 100,000 50.000 x 10° to < 100.000 x 10°	25,000 to < 50,000 25.000 x 10 ⁹ to $< 50.000 x 10^{9}$	< 25,000 < 25.000 x 10°
PT, High (not on anticoagulation therapy	1.1 to < 1.25 x ULN	1.25 to < 1.50 x ULN	1.50 to < 3.00 x ULN	\geq 3.00 x ULN
WBC, Decreased (cells/mm ³ ; cells/L) > 7 days of age	2,000 to 2,499 2.000 x 10° to 2.499 x 10°	1,500 to 1,999 1.500 x 10° to 1.999 x 10°	1,000 to 1,499 1.000 x 10° to 1.499 x 10°	< 1,000 < 1.000 x 10°
\leq 7 days of age	5,500 to 6,999 5.500 x 10° to 6.999 x 10°	4,000 to 5,499 4.000 x 10 ⁹ to 5.499 x 10 ⁹	2,500 to 3,999 2.500 x 10° to 3.999 x 10°	< 2,500 < 2.500 x 10°

Urinalysis

PARAMETER	GRADE 1 MILD	GRADE 2 MODERATE	GRADE 3 SEVERE	GRADE 4 POTENTIALLY LIFE- THREATENING
Glycosuria (random collection tested by dipstick)	Trace to 1+ or ≤250 mg	2+ or > 250 to $\leq 500 \text{ mg}$	>2+ or > 500 mg	NA
Hematuria (not to be reported based on dipstick findings or on blood believed to be of menstrual origin)	6 to < 10 RBCs per high power field	\geq 10 RBCs per high power field	Gross, with or without clots OR With RBC casts OR Intervention indicated	Life-threatening consequences
Proteinuria (random collection tested by dipstick)	1+	2+	3+ or higher	NA

DAIDS, 2017

10.3. Appendix 3: Liver Safety: Required Actions, Follow-up Assessments and Study Intervention Restart Guidelines

Study treatment refers to all drugs evaluated in the study and therefore includes ViiV study intervention and non-ViiV ART therapies that can be used in combination with ViiV products or other ART interventions.

A liver stopping event is an occurrence of predefined liver chemistry changes (ALT, bilirubin and or INR) that trigger discontinuation of study treatment and requirement of additional actions and follow up assessments to be performed.

A liver monitoring event is as an occurrence of predefined liver chemistry changes (ALT, bilirubin and or INR) that triggers increased monitoring of the participant's liver chemistries, but no action is taken with study treatment unless liver chemistry stopping criteria are met.

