The Division of AIDS Table for Grading the Severity of Adult and Pediatric Adverse Events ("DAIDS AE Grading Table") is a descriptive terminology which can be utilized for Adverse Event (AE) reporting. A grading (severity) scale is provided for each AE term.

Estimating Severity Grade for Parameters Not Identified in the Grading Table

The functional table below should be used to grade the severity of an AE that is not specifically identified in the grading table. In addition, all deaths related to an AE are to be classified as grade 5.

PARAMETER	GRADE 1 MILD	GRADE 2 MODERATE	GRADE 3 SEVERE	GRADE 4 POTENTIALLY LIFE-THREATENING
Clinical adverse event NOT identified elsewhere in the grading table	Mild symptoms causing no or minimal interference with usual social & functional activities with intervention not indicated	Moderate symptoms causing greater than minimal interference with usual social & functional activities with intervention indicated	Severe symptoms causing inability to perform usual social & functional activities with intervention or hospitalization indicated	Potentially life-threatening symptoms causing inability to perform basic self-care functions with intervention indicated to prevent permanent impairment, persistent disability, or death

Major Clinical Conditions Cardiovascular

PARAMETER	GRADE 1 MILD	GRADE 2 MODERATE	GRADE 3 SEVERE	GRADE 4 POTENTIALLY LIFE- THREATENING
Arrhythmia (by ECG or physical examination) Specify type, if applicable	No symptoms AND No intervention indicated	No symptoms AND Non-urgent intervention indicated	Non-life-threatening symptoms AND Non-urgent intervention indicated	Life-threatening arrhythmia OR Urgent intervention indicated
Blood Pressure Abnormalities ¹ Hypertension (with the lowest reading taken after repeat testing during a visit) ≥ 18 years of age	140 to < 160 mmHg systolic OR 90 to < 100 mmHg diastolic	≥ 160 to < 180 mmHg systolic OR ≥ 100 to < 110 mmHg diastolic	≥ 180 mmHg systolic OR ≥ 110 mmHg diastolic	Life-threatening consequences in a participant not previously diagnosed with hypertension (e.g., malignant hypertension) OR Hospitalization indicated

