13.5.4. Safety

Adverse Events
DAIDS Grading

 Clinical adverse events will be graded based on the Division of AIDS Table for Grading the Severity of Adult and Pediatric Adverse Events Version 2.1, March 2017, as specified in the protocol Appendix 10.2. If a grade value is expected per DAIDS but is missing in the eCRF, then the missing grade will be given an ordinal grade value of -1 for determining the maximum grade within and across preferred terms. For example:

Adverse Events

 • if a participant has two separate instances of the same preferred term, one with grade 2 and one with missing grade, then the maximum grade for the preferred term will be set to grade 2. • if a participant reports two different AE preferred terms overall, one with grade 1 and one with missing grade (where a DAIDS grade is expected), then the maximum grade across preferred terms (i.e. in the ANY EVENT row) will be set to grade 1. • If a participant reports only one AE overall and this has a missing grade (where a DAIDS grade is expected), then this will be presented under a grade = missing category
Days since First Dose (Days)

 • AE Start Date – Intervention Phase Treatment Start Date + 1
Days since Last Dose (Days)

 • AE Start Date – Date of Last Dose of Study Treatment (Oral CAB+RPV, SOC bridging, CAB/RPV IM Injection) prior to/on the Start Date of AE + 1
Days since Phase Start

 • For AEs in Intervention/Extension Phase: 
 ○ AE Start Date - Intervention Treatment Start Date + 1 • For AEs in Long-term Follow-up Phase: 
 ○ AE Start Date – LTFU ART Start Date
Duration (Days)

 • AE Resolution Date – AE Start Date + 1
Drug-related

 • If relationship is marked 'YES' on Inform/eCRF • Injection site reactions will be considered as drug-related if the relationship to study drug value is missing in the eCRF.
Laboratory Parameters

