
 • If a laboratory value which is expected to have a numeric value for summary purposes, has a non-detectable level reported in the database, where the numeric value is missing, but typically a character value starting with '<x' or '>x' (or indicated as less than x or greater than x in the comment field) is present, the number of significant digits in the observed values will be used to determine how much to add or subtract in order to impute the corresponding numeric value. If a character value starting with "<=x", then the numeric value will be x. 
 ○ Example 1: 2 Significant Digits = '< x' becomes x – 0.01 ○ Example 2: 1 Significant Digit = '> x' or '>=x' becomes x + 0.1 ○ Example 3: 0 Significant Digits = '< x' becomes x – 1
Lab Toxicities – DAIDS Grading

 • Toxicities will be based on the Division of AIDS (DAIDS) grading system, Version 2.1, March 2017, as specified in the protocol of Appendix 10.2 • Toxicity grades provided by the central laboratory do not distinguish between abnormally high or low criteria, when both are relevant for a particular parameter.

Other Safety Endpoints
Extent of Exposure

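### As printed, the adult total bilirubin row leaves larger asymptomatic rises with no grade, so SAP Table 3.42 followed literally would under-report them (minor)

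*Protocol*

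**What the plan says.** Protocol Section 10.2 reproduces the DAIDS grading table. For total bilirubin above 28 days of age, Grade 1 is 1.1 to <1.6x ULN and Grade 2 is "1.6 to < 2.6 x ULN", with no clinical condition. Grade 3 is "2.6 to < 5.0 x ULN with other signs and symptoms of hepatotoxicity". Grade 4 is 5.0x ULN or more, again only with a clinical condition, here life-threatening consequences.

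The direct bilirubin row has no Grade 1 or 2. Its Grade 3 is "> ULN with other signs and symptoms of hepatotoxicity", and its Grade 4 also needs life-threatening consequences.

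SAP 13.5.4 adopts the table for laboratory data: "Toxicities will be based on the Division of AIDS (DAIDS) grading system, Version 2.1, March 2017, as specified in the protocol of Appendix 10.2". SAP 13.7 points to the same protocol section for abnormal laboratory values. SAP 13.5.4 adds that "Toxicity grades provided by the central laboratory do not distinguish between abnormally high or low criteria", which implies that the laboratory supplies grades, but neither document gives its rule for bilirubin. Table 3.42, due at headline, Month 12 and end of study, summarises chemistry by maximum grade increase over baseline.

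**The concern.** A severity scale should not rank a larger abnormality below a smaller one. Here a value just under 2.6x ULN is Grade 2, while an asymptomatic value of 2.6x ULN or more has no grade at all. Because Table 3.42 takes the highest grade after baseline, the ungraded value can vanish behind a smaller graded one, and the reader sees no gap. If every raised value in a participant is ungraded, the SAP does not say how that participant is shown.

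The row is used beyond that table. Exclusion criterion 22 (protocol 5.2) turns on a verified Grade 4 laboratory abnormality. Protocol 10.6.3 and 10.6.4 set out what to do with asymptomatic Grade 3 and Grade 4 laboratory values, a state that total bilirubin cannot reach as printed. Under protocol 10.5.1, clinically significant laboratory abnormalities are adverse events, and protocol 10.6 has adverse events graded from the same table. Adverse event severity is a secondary endpoint (protocol Section 3).

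**Working it through.** **Inputs.** The four adult total bilirubin cells of protocol 10.2 are coded as printed: Grade 1 if 1.1 to <1.6x ULN; Grade 2 if 1.6 to <2.6; Grade 3 if 2.6 to <5.0 and signs or symptoms of hepatotoxicity; Grade 4 if 5.0 or more and life-threatening consequences; otherwise none. The comparison uses the same bands with the clinical conditions removed. The plan states no figure to reproduce.

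| Total bilirubin (x ULN) | As printed, no symptoms | As printed, symptoms, not life-threatening | As printed, life-threatening | Bands alone |
|---|---|---|---|---|
| 1.2 | 1 | 1 | 1 | 1 |
| 2.0 | 2 | 2 | 2 | 2 |
| 2.59 | 2 | 2 | 2 | 2 |
| 2.6 | none | 3 | 3 | 3 |
| 4.0 | none | 3 | 3 | 3 |
| 4.99 | none | 3 | 3 | 3 |
| 5.0 | none | none | 4 | 4 |
| 6.0 | none | none | 4 | 4 |

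There are two gaps: 2.6 to <5.0x ULN without symptoms, and 5.0x ULN or more without life-threatening consequences. On the bands alone, every value from 1.1x ULN upward has exactly one grade.

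**Effect on Table 3.42.** Take a participant with a normal baseline, then 2x ULN, then 4x ULN without symptoms. As printed, the grades are 2 and none, so the maximum is 2. On the bands alone they are 2 and 3, so the maximum is 3.

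**Does another rule fill the gap?**
- The fallback table opening protocol 10.2 does not: "The functional table below should be used to grade the severity of an AE that is not specifically identified in the grading table". Total bilirubin is identified.
- The direct bilirubin row does not, because its only grades carry the same kind of clinical condition.
- The SAP 13.5.4 rule that "the missing grade will be given an ordinal grade value of -1 for determining the maximum grade within and across preferred terms" sits under adverse events, not laboratory parameters.

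**Is this usual for the panel?** Protocol 8.4.4 lists 16 clinical chemistry analytes. BUN and chloride have no row in 10.2, which leaves 14 (reading total CO2 as bicarbonate). Thirteen of those reach their highest grade on the number alone; lipase Grade 3, for example, is simply "3.0 to < 5.0 x ULN". Total bilirubin is the one that does not.

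**Where the values still appear.** Table 3.40 (change from baseline), Figure 3.4 (maximum total bilirubin against maximum ALT) and the end-of-study data viewer do not depend on grade. Table 3.47 and Listings 41 and 42 are only a partial safeguard. Under SAP 13.7.1, bilirubin of at least 2x ULN counts only if the direct fraction is at least 35% when direct bilirubin is available, and protocol 8.4.4 runs it reflexively above 1.5x ULN. So 4x ULN with a 40% direct fraction is counted in the Table 3.47 bilirubin row, whereas 4x ULN with 20% is not, and has no grade in Table 3.42 either.

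**The case against.** The strongest reply is that no effect has been shown. The central laboratory appears to supply grades, and the documents describe no route by which it would learn of symptoms, so it may well grade on the number. If so, Table 3.42 is right and only the written rule is wrong. This stands, and it limits the size of the point. It does not remove it, because the SAP binds the grade to the printed row and the laboratory's rule is not given.

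A second reply is that the table is the DAIDS scale, adopted and not designed by the sponsor. That is fair. Whether the printed row matches its source cannot be checked from these documents, so a reader should not infer either a copying error or a flaw in DAIDS.

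A third is that leaving a raised bilirubin ungraded without clinical findings is already the pattern in the direct bilirubin row, and that isolated indirect rises can be benign. The direct row, however, grades nothing on the number alone, so a larger value never falls below a smaller one. The total bilirubin row does create that reversal. The remark about benign rises stands and is met in the fix.

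A reader might also infer that a hepatic signal would be hidden, or that liver stopping would fail. The documents do not support this: the liver stopping criteria in protocol 10.3.1 rest on their own ALT-based thresholds, not on DAIDS grade, and several displays show the values ungraded.

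**Conclusion.** The gap is real in the text, and no other rule in either document closes it. Followed as written, Table 3.42 would show some larger asymptomatic total bilirubin rises at a lower grade than the numeric bands give, or at none. This is a minor point.

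It would be tempting to call the effect a matter of displays only, with no endpoint touched. On the literal reading that is too narrow, because exclusion criterion 22, protocol 10.6.3 and 10.6.4, and adverse event grading all draw on the same row. It would equally be too strong to say that results will be wrong. The number of participants affected is unknown, and for Table 3.42 it is zero if the laboratory grades on the number. The conclusion assumes that the row is printed as the sponsor intends; each cell carries its own complete text, so it does not look like a conversion fault.

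**What to change.** 1. Check the total bilirubin row in protocol 10.2 against the DAIDS version 2.1 source. If it is a transcription slip, correct the appendix, which also settles eligibility, management and adverse event grading.
2. In SAP 13.5.4, state that total bilirubin is graded for laboratory displays on the printed ULN bands alone: 1.1 to <1.6 = Grade 1; 1.6 to <2.6 = Grade 2; 2.6 to <5.0 = Grade 3; 5.0 or more = Grade 4. If the row does match its source, record this as a departure for displays.
3. Confirm that the central laboratory applies the same bands.

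Note with Table 3.42 only that isolated indirect rises may show as Grade 3 or 4, for example in Gilbert's syndrome, which exclusion criterion 12 admits. Do not add a SAP footnote ruling on exclusion criterion 22 or Appendix 6. A table footnote cannot settle participant management, and protocol 10.6.3 and 10.6.4 already allow asymptomatic Grade 3 or 4 laboratory values to continue on treatment after discussion with the Medical Monitor, where there is compelling evidence that study drug is not the cause.

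The cost is one source check, a sentence or two in the SAP and one query to the laboratory, plus a correction to the protocol appendix if the check finds a slip. No new data are needed. The downside is that a few benign rises will carry a high displayed grade.
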